*** Medical Equipment for Human Subjects and Laboratory Animals; Investigational Devices ***

5. Medical Equipment for Human Subjects

If medical equipment is being used for human subjects/patients, describe this equipment and indicate if the use is normal practice for the population under study. You may have already described this equipment in the Study Procedures section. If you have already listed this information in the Study Procedures Section, please do not duplicate this information here. In the space below, input N/A if not applicable, indicate if this is already listed in the Study Procedures Section, or describe the equipment.

N/A

6. Investigational Devices

Please list in the space below all Investigational Devices to be used on Subjects.

Investigational Devices

Investigational Devices

Describe the device(s) to be used

ActivaDose II Iontophoresis Delivery Unity

Device Name ActivaDose II Iontophoresis Delivery Unity

Manufacturer ActivaTek, Inc.

Significant risk

Y

Non-Significant risk

IDE #

Rationale for Non-Significant Risk Device

Class 2 device.

If a non-significant risk device study is indicated, provide rationale for the device being non-significant risk. Please state if you need IRB guidance on whether this is a significant or non-significant risk device.

* * * Drugs, Reagents, or Chemicals * * *

7. Drugs, Reagents, or Chemicals

- a) Please list in the space below all investigational drugs, reagents or chemicals to be administered to subjects during this study.

- b) Please list in the space below all commercial drugs, reagents or chemicals to be administered to subjects during this study.

Please read the IND Statements

* * * Subject Population (a-g) * * *

8.

Subject Population - In the space below, please detail the participants that you are requesting to recruit (include requested participant number and description of each group requested). (Input N/A if not applicable)

a) **Requested Participant Description (Include number of participants that you plan to study and description of each group requested, if applicable).**

N/A

b) **What is the rationale for studying the requested group(s) of participants?**

To investigate the effects of tDCS on leg muscle strength and fatigue. The research team has experience with all the methods involved.

c) If applicable, state the rationale for involvement of potentially vulnerable subjects to be entered into the study, including minors, pregnant women, economically and educationally disadvantaged, or decisionally impaired subjects. Specify the measures being taken to minimize the risks and the chance of harm to the potentially vulnerable subjects.

N/A

d) If women, minorities, or minors are not included, a clear compelling rationale must be provided. Examples for not including minors: disease does not occur in children; drug or device would interfere with normal growth and development; etc.

N/A

e) State if any of the subjects are students, employees, or laboratory personnel. They should be presented with the same written informed consent. If compensation is allowed, they should also receive it.

N/A

f) Describe how potential subjects will be identified for recruitment (e.g., chart review, referral from individual's treating physician, those individuals answering an ad). How will potential participants learn about the research and how will they be recruited (e.g., flyer, email, web posting, telephone, etc.)? Attach recruitment materials in the Attachment Section (#16). Important to remember: potential subjects may not be contacted before IRB approval.

Prospective participants will be recruited from the Integrative Neurophysiology Laboratory's (INPL) participant database, the clinical practice of [name], Banner Health, Greeley CO, and through advertisements in the Colorado and Wyoming Chapter of the National MS Society newsletters. All experimental procedures will be performed in the INPL (Director: [name], FACSM). Interested individuals will perform an initial screening via an online questionnaire, hosted by Qualtrics, which has a contract with the College of Health and Human Sciences. Contact information for the prospective participants' information will be accessible only to the research staff according to HIPPA regulations. After completion of the online screening form, INPL personal will contact eligible participants via phone. INPL staff will schedule the participants' first visit (30 total).

g) If applicable, provide rationale for the inclusion of healthy volunteers in this study. Specify any risks to which these healthy volunteers may possibly be exposed. Specify the measures being taken to minimize the risks and the chance of harm to these volunteers.

N/A

* * * Subject Population (h-m) * * *

8. Subject Population (Input N/A if not applicable)

h) Inclusion and Exclusion Criteria (e.g., Participants must have 20/20 vision, Participants must be 30-45 years of age, etc.)

Identify inclusion criteria.

Medically diagnosed with MS, 30-60 years of age, Moderate disability (Patient Determined Disease Steps score 2-6), self-reported differences in function between the legs (2-5 on a 1-5 scale).

Identify exclusion criteria.

- A relapse of disease symptoms in the last 60 days
- A condition unrelated to MS that would exacerbate fatigue, such as anemia, hypothyroidism, shiftwork-related fatigue, B12 deficiency, major sleep disorder, or major depressive disorder
- Medical diagnosis or condition that makes participating in exercise training dangerous, such as major renal, pulmonary, hepatic, cardiac, gastrointestinal, HIV, cancer (other than treated basal cell cancer), other neurological disorders, or pregnancy
- History of heart attack or current diagnosis of cardiovascular disease
- History of seizure disorders (or on medications known to lower seizure threshold),
 - Hydrocephalus (i.e. buildup of fluid in the brain)
- Alcohol dependence or abuse (>2 drinks/day), or present history (last six months) of drug abuse
- History of significant traumatic brain injury
- Pregnancy
- Recent hospitalization (within the last 3 months) or enforced bed rest/sedentary state.
- Presence of metal is present or implanted device or metal object that is not safe for TMS.
- Presence of holes or fissures of the cranial bones

i) Describe your screening procedures. Attach your screening document(s) (e.g., health history questionnaire) in the Attachment Section (#16).

Prospective participants will be screened via an online questionnaire. This questionnaire will gather contact information, date of birth, height, weight, self-reported disability status, and cardiovascular risk factors.

j) Describe how you will be cognizant of other protocols in which subjects might be participating. Please explain if subjects will be participating in more than one study.

This will be the only study participants will be in.

k) Compensation. Explain the amount and schedule of compensation, if any, that will be paid for participation in the study. Compensation includes food, gift cards, money, tokens, etc. Include provisions for prorating payment, if applicable. Compensation should be prorated if several activities are involved for different time periods (e.g., \$10 for session #1, and \$10 for session #2).

Subjects in the fatigue group will be compensated \$20 upon completion of the study.

l) Costs. Please explain any costs that will be charged to the subject.

None, participants are only responsible for their transportation to/from campus.

m) Estimate the probable duration of the entire study. This estimate should include the total time each subject is to be involved and the duration the data about the subject is to be collected (e.g., This is a 2-year study. Participants will be interviewed 3 times per year; each interview will last approximately 2 hours. Total approximate time commitment for participants is 12 hours). These times should be consistent with the time commitment listed on the consent document.

Participants will be expected to spend approximately 2.5-3 hours split over 2 sessions. We expect data collection to last 6 months.

* * * Risks * * *

9. Risks (Input N/A if not applicable)

US Department of Health & Human Services (HHS) Regulations define a subject at risk as follows: "...any individual who may be exposed to the possibility of injury, including physical, psychological, or social injury, as a consequence of participation as a subject in any research, development, or related activity which departs from the application of those accepted methods necessary to meet his needs, or which increases the ordinary risks of daily life, including the recognized risks inherent in a chosen occupation or field of service."

a) PI's evaluation of the overall level of Risk. (Please check one: minimal or > minimal.)

Y Minimal (everyday living)
 > Minimal (greater than everyday living)

b)

For the following categories include a scientific estimate of the frequency, severity, and reversibility of potential risks. Wherever possible, include statistical incidence of complications and the mortality rate of proposed procedures. Where there has been insufficient time to accumulate significant data ON risk, a statement to this effect should be included. (In describing these risks in the consent form to the subject, it is helpful to use comparisons which are meaningful to persons unfamiliar with medical terminology.) Address any risks related to:

1. Use of investigational devices. Please include the clinical adverse events (AEs) associated with each of the devices with an indication of frequency, severity and reversibility. This information can often be found in the Investigator(s) brochure.

N/A

2 Use of investigational drugs. Please include the clinical AEs associated with each of the drugs with an indication of frequency, severity and reversibility. This information can often be found in the Investigator(s) brochure.

N/A

3 Use of commercially available drugs, reagents or chemicals. Please include the clinical AEs associated with each of the drugs with an indication of frequency, severity and reversibility. This information can often be found in the package insert provided by the manufacturer.

N/A

4 When performing procedures, please include all investigational, non-investigational and non-invasive procedures (e.g., surgery, blood draws, treadmill tests).

Participants will perform maximal voluntary strength tests with the leg extensors, -flexors, and dorsiflexors and a 6 min walk test to determine how far they can walk in 6 min. They will also perform a fatigue task (isometric contraction) with the more affected leg. There is a risk of muscle/tendon strain with the exercises.

5 Radioisotopes/radiation-producing machines(e.g., X-rays, CT scans, fluoroscopy).

c)

For the following categories, include an estimate of the potential risk, if applicable.

1. Physical well-being.

Potential risks include: skin irritation to surface electromyography electrodes, muscle cramps/spasms during strength testing.

tDCS safety

tDCS is a non-invasive brain stimulation technique in which a very weak electrical current is applied to the scalp. tDCS has been conducted on humans and animals for many years and no evidence has emerged to suggest that it is harmful or has ever induced a serious side effect. However, the safety of tDCS is dependent on current strength, electrode size, and stimulation duration. Accordingly, these parameters have been investigated to establish safe and effective stimulation parameters for tDCS applications in research involving human subjects. The only side effects that have been reported when proper guidelines are followed are temporary tingling, itching, headache, or skin redness under the electrodes in some subjects. For example, a 2008 review of the approximately 100 human tDCS studies up until that time on healthy adults and patients found that 64 of these studies reported no side effects, 24 studies reported a temporary itching or tingling under the electrodes in some subjects, and one study reported skin redness. Furthermore, these slight side effects were of equal occurrence in subjects that received placebo stimulation in 7 studies. In addition, only two subjects in these 100 studies reported a mild headache. Similar findings have recently been reported in research and review articles (Nitsche et al. 2008; Hummel et al. 2008).

Physiological studies have also assessed the safety of tDCS when applied within the aforementioned stimulation guidelines. For example, there was no neuronal damage as measured by serum neuron-specific enolase (Stagg & Nitsche, 2011) or MRI measures of edema using contrast enhanced and diffusion-weighted MRI measures following administration of tDCS (Nitsche et al. 2004). Furthermore, tDCS did not negatively alter measures of neuropsychological function and EEG activity (Iver et al. 2005). Accordingly, rat studies using tDCS models emulating tDCS applied to humans (Liebetanz et al. 2009) showed that the current density needed to induce tissue damage or lesions was about 1429 mA/cm², whereas the current densities used in human studies are between 0.04 and 0.08 mA/cm² and in this proposal are 0.029 mA/cm². In conclusion, the tDCS stimulation parameters in this study are identical to the most common in the literature and have been proven to be exceptionally safe and well-tolerated.

The probability is very unlikely that harm may occur (see above). Based on the available literature a slight headache should be the worst possible negative effect and should be very rare. In this case, non-prescription medication should relieve the headache within 1-2 hours.

Risks will be minimized by using safe, well-established procedures and strict monitoring of each experimental session. Risks are minimized by using stimulation parameters that are well-described, within international guidelines, and within the range of those used in hundreds if not thousands of studies (see above).

TMS safety

TMS is a non-invasive brain stimulation technique that can be used for both diagnostic and therapeutic procedures. The single and paired-pulse TMS techniques performed in this study have been used extensively in thousands of research studies and on tens of thousands of subjects in the United States and around the world. Single and paired pulse TMS techniques are considered very safe (Hallet, 2000, 2007) when accepted guidelines are followed (Wassermann et al. 1998). Finally, no long-term risks have been reported in the aforementioned review articles involving the use of TMS. In general, the risks associated with TMS are very minimal (Anand et al. 2002; Anderson et al. 2006; Loo et al. 2008). There is a very small risk of seizures if rTMS is done with very intense, high frequency stimulation or with trains of stimulation separated by a second or less (Anand et al. 2002; Anderson et al. 2006; Loo et al. 2008). Such intensity, frequency and repetition rate will not be used in this study as the study does NOT include rTMS and only single and paired pulse TMS methods will be employed. For most people, the single and paired pulse stimulation is not painful, but

occasionally slight discomfort or headache can occur. The headaches go away quickly with nonprescription medication. The noise caused by TMS pulses may affect hearing; therefore, subjects will be fitted with earplugs during TMS testing. Finally, there is no medical risk associated with the surface EMG recordings of the muscle responses to TMS.

2. **Psychological well-being.**

None

3. **Economic well-being.**

None

4. **Social well-being.**

None

d) In case of overseas research, or working with a specific race/ethnicity in the United States, provide background on what experience the Investigator(s) have with the proposed population. Describe qualifications/preparations that enable the Investigator(s) to evaluate cultural appropriateness and estimate/minimize risks to subjects.

N/A

e) Special Precautions. Describe the planned procedures for protecting against or minimizing potential risks. If appropriate, include the standards for termination of the participation of the individual subject. Discuss plans for ensuring necessary medical or professional intervention in the event of adverse effects to the subjects.

All research staff are certified in CPR, AED, and First Aid by the American Red Cross. Participants are freely available to stop any procedure at any time.

f)

Data Safety Monitoring

N Is there a Data Safety Monitoring Board (DSMB)?

If yes, describe its role and indicate who set up the Data Safety Monitoring Board (e.g., sponsor or Protocol Director).

Describe the data and safety monitoring plan developed to ensure the safety of participants and the validity and integrity of research data. Monitoring should be commensurate with risks and with the size and complexity of the trials.

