1. Summary: Number of Participants Associated with the Protocol:

a. Total number of participants approved to date:

40 (20 strength and 20 fatigue)

b. Number of participants studied since the last approval date:

5 (1 strength and 4 fatigue)

c. Total number of participants studied since the beginning of the project:

5 (1 strength and 4 fatigue)

d. Number of participants remaining to study (total number of participants approved LESS the total number of participants studied to date):

35

e. Please explain if there is a discrepancy in participant numbers (e.g., more participants responded to a survey than had been approved):

n/a

2. a. Reasons and number of withdrawals from the research (both subject and investigator initiated) since the last approval date.

none

b. **Number of subjects lost to follow-up since the beginning of the study.**
none

c. **Please summarize any protocol deviations/violations or unanticipated problems (UPs)/adverse events (AEs) since the last continuing review or original approval (if this is your first continuing review). Please indicate if any of the unanticipated problems/events are being reported to the IRB for the first time. If you have or will make changes to your protocol as a result of any unanticipated problem/event or adverse event, please summarize those changes in Question #5 below.**
none

e. **Complaints about the research during the last year.**
none

3. **A summary of any recent findings, literature, or other relevant information (especially pertaining to risks), if applicable.**
none

4. **Description of the remainder of project:**

Y **Do you plan to recruit more subjects?**

If "No," have all subjects completed all research-related interventions? Note: Protocols must be renewed to continue recruiting participants and/or collect data from already recruited participants.

N **Are you only performing data analysis? NOTE: If you are analyzing data with no identifiers (i.e., you cannot link your data to individuals), you can close your protocol by submitting a Final Report.**

N **Does this protocol have a Data Safety Monitoring Board (DSMB)?**

If you do have a DSMB, have reports been submitted to the IRB and/or the Sponsor? Upload any DSMB reports that have not yet been submitted to the IRB since the approval or last continuing review.

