5. **Summarize all approved changes in the protocol since the last continuing review or since the original approval (if this is your first continuing review). For example: Have you amended your protocol during the past year? Are you requesting to make any changes for the upcoming year? Have you included any changes as a result of an unanticipated problem/event or Adverse events (AE)? Have there been any personnel changes in the past year (including a change in department head)?**

Amendment 1: Added clinicaltrials.gov language to the consent
Amendment 2: Removed the requirement of physician clearance and updated screener to mimic other tDCS protocol
Amendment 3: Add compensation for fatigue group and the strength group was closed to enrollment. Please note: the investigator would like to keep the strength group open to enrollment, please revise in the next approval letter.

If necessary, proceed to the appropriate section(s) of the protocol and make your requested changes. Remember that if you are requesting to revise a document that is already attached, you must delete the already attached document and upload the revised document.

6. List of Protocol Sections (and questions) that have been changed/modified.

Updated [name]'s personnel status

Please note: the investigator would like to keep the strength group open to enrollment, please revise in the approval letter.

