a) In lay language, describe all the procedures, from screening through end-of-study, that the human subject must undergo in the research project, including study visits, drug treatments, randomization and the procedures that are part of standard of care. Please note: Do NOT respond "See Attachment Section." If you would like to add tables, charts, etc., attach those files in the Attachment section (#16).

To investigate the effects of tDCS on strength and fatigue of the leg muscles in patients with multiple sclerosis (MS) we will employ a randomized blinded cross-over design. Once accepted into the study participants will be randomized into 1 of 4 groups. Group 1 and 2 will perform leg strength testing followed by a 6 minute walk test. Groups 3 and 4 will perform a fatigue task. Each group will perform the same procedures during 2 different visits with 1 visit having a tDCS sham procedure performed and 1 visit performing the task with tDCS. The order of the sham / treatment will be based on the participant's group assignment. Each visit will be separated by at least 7 days. See attachment for proposal timeline.

Participant Recruitment:

Prospective participants will be recruited from the: Integrative Neurophysiology Laboratory's (INPL) participant database; the clinical practice of [name], Banner Health, Greeley CO; and through advertisements in the Colorado and Wyoming Chapter of the National MS Society newsletters. All experimental procedures will be performed in the INPL (Director: [name], FACSM). Interested individuals will perform an initial screening via an online questionnaire, hosted by Qualtrics, which has an agreement with the College of Health and Human Sciences. Contact information for the prospective participants' information will be accessible only to the research staff according to HIPPA regulations. After completion of the online screening form, INPL personnel will contact 40 eligible participants, 10 for each group, via phone to confirm their participation and schedule the participant's first visit. Once eligibility is confirmed participants will be randomly assigned to 1 of the 4 groups using a random number generator. If by chance a group fills, 10 participants assigned, before the others that number will then be removed to ensure each group has a similar size.

Experimental Sessions:

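### Section 8(f) schedules 30 first visits where Section 2(a) plans 40 and 40 were approved; 30 cannot fill four groups of 10

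*Combined protocol and SAP*

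**What the plan says.** Three places give a planned number.

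- Section 2(a), Participant Recruitment: "INPL personnel will contact 40 eligible participants, 10 for each group, via phone", to confirm participation and schedule the first visit.
- Continuing review summary, item 1a, approved to date: "40 (20 strength and 20 fatigue"). Item 1c gives "5 (1 strength and 4 fatigue") studied, and item 1d gives 35 remaining.
- Section 8(f), describing the same telephone contact and scheduling: "first visit (30 total"), with no split by task or group.

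Section 8(a), where the requested number belongs, is answered N/A, so it does not settle the matter.

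On allocation, Section 2(a) says: "Once eligibility is confirmed participants will be randomly assigned to 1 of the 4 groups using a random number generator". The cap follows: "If by chance a group fills, 10 participants assigned, before the others that number will then be removed". The stated aim of this rule is "to ensure each group has a similar size". Groups 1 and 2 are strength and groups 3 and 4 fatigue. Within each pair, one group has tDCS first and the other sham first. The supplied text contains no statistical analysis section and no justification for either 40 or 30.

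**The concern.** The two figures stand in current text for the same step, so a reader cannot tell from the protocol alone how many people each task is meant to have. The total also matters to the allocation rule, which forces equal groups only by filling them. If enrolment stops before the groups fill, both the size of each task and the balance of treatment order are left to chance.

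Task size determines what each paired tDCS-sham comparison can detect. Order balance matters because familiarisation between the two visits cancels from a simple paired mean only when the two orders are equal. The strength measure is partly protected, since maximal contractions are also taken before stimulation in each session. Walk distance is measured only after stimulation, and time to task failure only in a task that begins 5 minutes into it, so neither has a same-day baseline.

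**Working it through.** **1. The plan's own figure.** 4 groups × 10 = 40, and 20 + 20 = 40. 40 approved − 5 studied = 35, as item 1d states. The figure of 30 does not reconcile: it is 10 fewer (25%), and 30 / 4 = 7.5 per group. An even split by task gives 15, which is odd, so order could be 8 v 7 at best.

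**2. The draw with all four groups open.** Assumption: each unfilled group is equally likely at each draw (the plan does not state the probabilities). At 30 assigned, the other task can hold at most 20, so a task has at least 30 − 20 = 10 people and at most 20. Exact enumeration for one task, with *a* people tDCS-first and *b* sham-first:

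| Assigned | People in task | a = b | Differ by ≥3 | Differ by ≥4 | Mean of abs(a−b)/(a+b) | Mean of 4ab/(a+b)² |
|---|---|---|---|---|---|---|
| 30 | 10–20 | 12% | 47% | 30% | 0.181 | 0.948 |
| 36 | 16–20 | 29% | 26% | 13% | 0.093 | 0.984 |
| 38 | 18–20 | 45% | 0 | 0 | 0.049 | 0.995 |
| 40 | 20 | 100% | 0 | 0 | 0 | 1 |

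At 30 assigned, a task has 11 to 19 people in 95% of draws and exactly 15 in 17%.

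**3. When the cap does balance order.** A task is 10 v 10 as soon as its own 20 places are filled. With all groups open this is certain in advance only at 40 assigned; at 30 a given task is already full in about 2% of draws. If strength is closed, the draw is between groups 3 and 4 alone, and fatigue reaches 10 v 10 at its own 20. The table does not apply to that case.

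**4. Task size.** Assuming a paired t-test, two-sided 5%, 80% power (the plan gives none of these), the detectable standardised difference is 1.00 at n = 10, 0.78 at 15 and 0.66 at 20.

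**5. Period effect.** Let τ be the tDCS-sham effect, π the second-session minus first-session change, and σ the SD of the paired difference within an order. The paired difference has mean τ − π in tDCS-first participants and τ + π in sham-first participants. Without a period term:

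- The estimate has mean τ − π(a − b)/(a + b). For 9 v 6 the share is 3/15 = 20%; the average at 30 assigned is 18%.
- The variance of the pooled paired differences is about σ² + π² × 4ab/(a + b)². At 10 v 10 with π = 0.5σ, the SD is √(1 + 0.25) = 1.12σ, so the error bars are about 12% too wide even in perfect balance.

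The widening outweighs the chance shift on average. In simulation with no treatment effect, a nominal 5% test and π = 0.5σ, false positives were about 4.4% at 30 assigned and about 3% at 10 v 10.

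With a period term the estimate has efficiency 4ab/(a + b)² and loses one degree of freedom. At n = 15 the detectable difference moves from 0.778 to 0.784 (8 v 7) or 0.799 (9 v 6).

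**The case against.** The best defence is that 40 is the approved number, Section 8(f) repeats Section 2(a) almost word for word, and 30 is probably a leftover. At 40 assigned, imbalance is zero before losses. This stands in part: 40 is the better-supported figure, but the other remains uncorrected.

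A reader might infer that the trial was heading for 30, or would stop short of 40, because only 5 had been studied 303 days after approval (25 October 2016 to 24 August 2017). The documents do not establish this. Amendments 2 and 3 were approved only 50 and 28 days before that report, and the date enrolment opened is not given. Amendment 3 closed strength, but "the investigator would like to keep the strength group open to enrollment", so neither state can be assumed. With strength closed, fatigue can reach 10 v 10 far short of 40 overall.

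A reader might also infer that unequal order biases the result or inflates false positives. It does not: which order is larger is chance, and omitting the period term makes the test conservative on average. The missing term is also only one part of an analysis description that is absent altogether, from a form whose supplied sections do not ask for one. The listed attachments are not reproduced.

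Finally, a reader might conclude that the draw should give way to permuted blocks within task. That is a trade-off. Blocks of 4 and 6 end 11 v 9 in about 22% of trials at the planned 20 per task, where the present rule gives exactly 10 v 10. They also make order more guessable (about 68%, against 59% at 40 assigned now).

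**Conclusion.** The conflict between 30 and 40 is real and needs correcting. Its consequence is conditional. If assignment stopped at 30 with all four groups open and equal draw probabilities, a task could have anywhere from 10 to 20 people, and order would differ by 3 or more in about 47% of trials. At 40, or once a task's own 20 places are filled, there is no imbalance before losses. The documents do not show which total was worked to, and they give no size for any period effect.

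The period term is a secondary point that does not depend on which total is right. Its value is mainly precision and correctly sized error bars, even at 10 v 10. It also removes the chance shift after early stopping or unequal losses.

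**What to change.** 1. Correct Section 8(f) to the approved 40. If 30 is intended, restate the total and the sizes per task and per group in Section 2(a) and in the continuing review summary, noting that 15 per task cannot be split equally by order. This is wording only.
2. When the cross-over analysis is written, include a period term in the tDCS-sham comparison. This needs no extra participants. It costs one degree of freedom and, under the present draw, about 5% of efficiency on average at 30 assigned, about 2% at 36, and no efficiency loss from imbalance at 10 v 10.

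No change to the randomisation method is needed on this point.
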